Phase 2: Implementation Cohort Evaluation	455-495 (Depending upon # performed during training phase)	
Safety Component
 
Primary endpoints:
 
 - Adverse events and device-related incidents 
Secondary endpoints:
 
 - Safety of procedure/removal - Provider perception of technical difficulty and complications during procedure and removal process 
Provider Acceptability Component:
 
 - Provider acceptability - Practicality of device use - Procedure and removal times 
Client Acceptability Component:
 
 - Client satisfaction - Cosmetic results - Comfort: 
 - During procedure to place device - During (nocturnal) erections - During removal 
Healing Component
 
 - Percentage of men clinically healed 49-52 days post placement (42 days post-removal) - Time at which point all men are clinically healed 	
Standardized forms to collect data on adverse events and device-related adverse events
 
Client records
 
Brief surveys to collect data on reasons to decline participation in the evaluation as indirect measure of acceptability
 
Brief surveys to collect data on client experience with the ShangRing as an indirect measure of acceptability
 
Qualitative interview with providers
 
Qualitative interviews with 50 male clients
 
Qualitative interview with providers
 
Brief surveys to collect data on reasons to decline participation in the evaluation as indirect measure of acceptability
 
Client records – including those recording application and removal times
 
Client records indicating healing per VMMC healing definition as completed by providers during day 49 healing assessment visit and subsequent weekly healing visits for those not healed at day 49
 
Photographs of the client's genital area, to be taken post-device removal (day 7), and at the day 49 healing assessment visit and at subsequent weekly healing visits

Evaluation Procedures and Logistics

Evaluation Offices

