The staff member will discuss the clinical course and AE with the client and encourage the client to return for review to the health facility where the circumcision procedure was performed, if deemed medically necessary. If the client does not return for follow-up visits deemed medically indicated, active tracing will be initiated. In situations where clients cannot be reached by telephone or located through physical tracing, after a total of 8 calls and 4 visits on different days, the case will be directed to the attention of the site manager for disposition. In this case, these clients will be considered to have experienced a moderate AE by default, unless follow-up indicating otherwise is able to be completed.

In-Person Qualitative Interviews

The evaluation staff will select 50 individuals to participate in a more in-depth in-person qualitative interview to be held 28 days post-circumcision. Fifty clients were chosen as the sample size, based on prior experience with evaluating acceptability of circumcision devices, which suggests that 50 is sufficient to obtain the necessary range of views and opinions. Only males aged 18 years or older will be eligible to be selected to participate in the qualitative interviews. All clients will be asked when they are enrolled if they are willing to participate in an interview. The first 50 clients, aged 18 years or older, to indicate willingness at enrollment to participate will be asked to interview. If after contacting these men for an interview, not all are able to participate, clinic staff will

continue to proceed down the list of clients in the order in which they enrolled and agreed to an interview, until 50 clients are selected. These interviews will be used to assess client pain, discomfort, and satisfaction with the procedure. Males selected for the qualitative interviews may refuse to participate or withdraw at any time, the reason for their refusal/withdrawal will be recorded and reported. Clients will be offered a small amount to reimburse their travel and time spent for the interview (estimated to be between 20-25 USD/45,000-56,500 Tanzanian Shillings but not to exceed 30 USD/67,900 Tanzanian Shillings).

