Participation in this evaluation is believed to pose no more than minimal risks. Potential complications of the ShangRing device circumcision include excessive bleeding, hematoma, infection, pain, wound dehiscence, injury to the glans or urethra, excessive or insufficient skin removal, and poor cosmetic results. The use of the ShangRing device has yielded low rates of adverse events in different studies. In a proof of concept evaluation in Kenya, all 40 procedures were completed successfully.³⁴ Only three mild adverse events, all cutaneous injuries of the skin of the penis, was reported among the 40 clients (7.5%) and mean pain scores were low. A second evaluation in Kenya enrolled 197 men, each of whom received successful ShangRing circumcisions, these were compared against 201 men who received conventional surgical circumcisions.³⁵ The ShangRing group experienced AEs at a similar rate to the conventional surgical circumcision group, with 14 moderate and one severe AE in the ShangRing group (7.6%) and 10 moderate AEs in the conventional surgical circumcision group (5.0%). The severe AE was a case of pain that occurred in the ShangRing group during the circumcision. The other AEs included: wound dehiscence, post-procedure pain, and an anesthetic complication. All AEs were

treated and resolved without problems. The pain scores between the two groups were similar at most points of time, with the exception that the pain during an erection while the device is in place was significantly higher for the ShangRing group. A comparative evaluation in Uganda found that a majority of men chose ShangRing over the dorsal slit method when asked to choose a preferred procedure, 508 chose ShangRing compared to 113 (though four men who chose ShangRing had to receive conventional circumcision when the ShangRing procedure failed, these failures occurred early in the evaluation and were attributed to provider inexperience).³⁶ There were no differences in the rate of moderate and severe AEs between the two groups – five total (1%) in the ShangRing group, and one (.9%) in the conventional surgical circumcision group. The AEs included post-operative pain, bleeding, infection, wound dehiscence, and insufficient skin removal. Additional studies in Kenya and Zambia have found similar rates of AEs between ShangRing procedures and conventional circumcision.³⁷

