Appendix X – ShangRing Post-Placement Survey

ShangRing Post-Placement Survey

[Table to be completed by Evaluation Staff]

Date (dd/mm/yyyy):	
Client ID:	
Name of Survey Administrator:	
Facility:	

Introduction: Thank you for agreeing to complete this survey to evaluate your experience with the ShangRing circumcision device. This survey asks a few brief questions about your experience in having the ShangRing device placed. Your name will not be recorded anywhere on this survey, and your replies will be kept completely confidential. In this survey there are no right or wrong answers. We are most interested in your honest opinions and reactions to these questions. You may also refuse to answer any question you wish for any reason. The information that you provide will help to determine the future use of ShangRing in Tanzania. If you have any questions about the survey, please do not hesitate to follow up with evaluation staff. If you have difficulty reading or understanding any of the questions, evaluation staff are on hand to read and help you interpret the questions.

1. Why did you choose to have a ShangRing circumcision instead of surgical circumcision (circle answer option below)?

I thought ShangRing would be less painful	I didn't want an injection	I had heard about ShangRing before	No Reason	Other (comment below)
Comment: _____				

2. How did you find the placement process for the ShangRing device (circle answer option below)?

It was about what I expected	It was easier than I expected	It was harder than I expected	I did not have any expectations for the placement	Other (comment below)
Comment: _____				

3. How did you find the pain of your circumcision during the ShangRing device placement (circle answer option below)?

It was about what I expected	It was less painful than I expected	It was more painful than I expected	I did not have any expectations about pain	Other (comment below)
Comment: _____				

4. At this point, would you recommend the ShangRing to someone you know who is considering circumcision (circle answer option below)?

Yes	No	I don't know at this time	Other (Comment below)
-----	----	---------------------------	-----------------------

Comment: _____

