Appendix XI – ShangRing Post-Removal Survey

ShangRing Post-Removal Survey

[Table to be completed by Evaluation Staff]

Date (dd/mm/yyyy):	
Client ID:	
Name of Survey Administrator:	
Facility:	

Introduction: Thank you for agreeing to complete this survey to evaluate your experience with the ShangRing circumcision device. This survey asks a few brief questions about your experience with ShangRing now that the device has been removed. Your name will not be recorded anywhere on this survey, and your replies will be kept completely confidential. In this survey there are no right or wrong answers. We are most interested in your honest opinions and reactions to these questions. You may also refuse to answer any question you wish for any reason. The information that you provide will help to determine the future use of ShangRing in Tanzania. If you have any questions about the survey, please do not hesitate to follow up with evaluation staff. If you have difficulty reading or understanding any of the questions, evaluation staff are on hand to read and help you interpret the questions.

1. How much discomfort did you experience while wearing the ShangRing device over the past seven days (circle answer option below)?

I had no discomfort while wearing the ring	I had minor discomfort while wearing the ring	I had moderate discomfort while wearing the ring	I had a lot of discomfort while wearing the ring	Other (comment below)
--	---	--	--	-----------------------

Comment: _____

2. How much did the ring affect you while performing day-to-day activities (circle answer option below)?

It did not affect me at all	It only affected me while performing certain activities	It affected me during all activities, but I could still do them	It prevented me from performing certain activities	Other (comment below)
-----------------------------	---	---	--	-----------------------

Comment: _____

3. After having worn the ring for a week, would you still choose to do ShangRing for circumcision, or would you choose surgery (circle answer option below)?

I would definitely choose ShangRing again	I would probably choose ShangRing again	I would probably choose surgery	I would definitely choose surgery	I don't know
---	---	---------------------------------	-----------------------------------	--------------

Comment: _____

(Survey is continued on next page)

4. How satisfied are you with the appearance of your circumcision (circle answer option below)?

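### Comfort during erections and during removal are listed as client endpoints, but no printed cohort form asks about erection discomfort after placement, and removal comfort rests on a poorly specified pain score.

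*Protocol*

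**What the plan says.** Table 2, Phase 2, Client Acceptability Component, lists comfort at three moments: during the placement procedure, "During (nocturnal) erections" and "During removal". The methods column names "Brief surveys to collect data on client experience with the ShangRing as an indirect measure of acceptability" and interviews with 50 male clients.

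The surveys are printed in full. Appendix X item 3 asks "How did you find the pain of your circumcision during the ShangRing device placement", with answers relative to expectation (as, less or more than expected, no expectation, other). Appendix XI item 1 asks "How much discomfort did you experience while wearing the ShangRing device over the past seven days", graded none, minor, moderate or a lot, plus other. Its remaining four items concern daily activities, choice of method, appearance and recommendation.

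The interview guide (Appendix XXII) has a probe on pain with erections under question 11 and an open question 12 on removal. On who is interviewed, In-Person Qualitative Interviews says: "Only males aged 18 years or older will be eligible to be selected to participate in the qualitative interviews".

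Potential Harm and Measures to Mitigate Harm summarises an earlier evaluation in Kenya that compared ShangRing with conventional surgery. Pain scores were similar at most times, except that "the pain during an erection while the device is in place was significantly higher for the ShangRing group".

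**The concern.** Two of the three listed comfort endpoints have no matching question in the surveys given to all clients, and the third is asked without an intensity scale. An answer that placement pain was about as expected fits both no pain and severe pain.

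Erection pain is the one pain outcome on which the protocol's own background evidence puts the device behind surgery. Clients are counselled to expect painful erections at night, fear of pain is named in the Introduction as a barrier to uptake, and the results are meant to inform policy and pre-procedure counselling. If the pilot cannot say how many clients had notable discomfort with erections, it leaves open a question it set itself and that future clients will ask. A later analysis plan cannot recover an item that was never asked.

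**Working it through.** **Step 1. Each listed moment against each printed client instrument.**

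| Instrument (who) | Placement | Erections, device in place | Removal |
|---|---|---|---|
| Appendix X survey (all) | Item 3, against expectation only | None | Not applicable |
| Appendix XI survey (all) | None | None specific; item 1 is general wear discomfort | None |
| Appendix IX device form (all) | Adverse event yes/no and severity | None | Not applicable |
| Appendix XII follow-up form (all) | Not applicable | None | Anesthesia needed; events or AEs during removal; pain score on photo frame, no field |
| Appendix XIV day-10 call (all) | None | None; asks about limiting or worsening pain | None |
| Appendix XVIII device events form (clients with a recorded event) | Pain event and VAS | Pain event and VAS, not tied to erections | Pain event and VAS |
| Appendix XXII interview (50 adults) | Question 10, open | Question 11, probe | Question 12, open |

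The ministry client form (Appendix VIII) does mention pain on erection, but as a complaint before the procedure.

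**Step 2. The removal pain score.** The follow-up form wants a pain score before and after removal shown on the photo frame. The form itself has no place to enter it. The Photography section lists the frame contents as subject number, date and evaluation day, with no pain score. The same section lets clients refuse photographs and stay in the evaluation. The score is therefore inconsistently specified and lost for anyone not photographed.

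**Step 3. The share covered by interviews.**
- Of the total sample: 50/575 = 8.7%.
- Of the Phase 2 row in Table 2 (575 - 120 = 455 to 575 - 80 = 495): 50/495 = 10.1% to 50/455 = 11.0%.

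**Step 4. What cohort items would give.** The protocol states no precision target for comfort. Its only such calculation is for adverse events: n = z²p(1-p)/d² = 1.96² × 0.02 × 0.98 / 0.015² = 334.6, rounded up to 335, which reproduces its figure. The same formula gives the 95% half-width, 1.96 × √(p(1-p)/n). The documents give no rate for erection discomfort, so p is assumed over a range:

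| Assumed p | n = 50 | n = 455 | n = 575 |
|---|---|---|---|
| 10% | ±8.3 points | ±2.8 | ±2.5 |
| 30% | ±12.7 | ±4.2 | ±3.7 |
| 50% | ±13.9 | ±4.6 | ±4.1 |

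The n = 50 column flatters the interviews. It treats them as a random sample giving coded answers. In-Person Qualitative Interviews takes the first 50 willing adults (Analysis Overview says random), and the data are analysed for themes.

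**The case against.** The strongest reply is that pain is captured for the whole cohort by other routes. Every client answers the wear-discomfort item. The device events form has a pain VAS and is to be completed for expected side effects as well as adverse events. Appendix XIX grades pain at placement, during wear and at or after removal, and its mild grade for wear and removal is low enough to take in an ordinary complaint. The follow-up form calls for a removal pain score. None of these routes has an age limit.

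This stands, and it rules out several stronger readings:
- A reader might infer that comfort is not measured in the cohort at all, or that no client gives structured data. The forms above contradict that.
- A reader might infer that nothing is collected on pain for ages 13-17. Only the interviews exclude them.
- A reader might take the Kenya comparison to be randomised, or part of this pilot. The section that reports it does not call it randomised, and this pilot has one arm.
- A reader might infer that a general answer of minor discomfort would be reported as good comfort. Nothing in the protocol says so.

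These routes still do not supply the erection endpoint. The VAS and the grades exist only when an event is recorded, so a missing record cannot separate no pain from not asked. The wear item cannot separate erections from the rest of the week.

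It is also fair to say that interviews are a stated method, that the Secondary Endpoints section does not name erection comfort, and that no proportion with an interval is promised. That makes this an improvement to data collection rather than an error in the analysis.

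**Conclusion.** The point holds in a limited form. As printed, erection comfort after placement is asked about directly only in open interviews of 50 adults, held on day 28, three weeks after removal. It cannot be given as a proportion of the cohort. Removal comfort has no survey item and depends on a score without a data field. Placement pain has a cohort survey answer but no patient-rated level outside event records.

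The size of the gap is the difference between themes from 8.7% of 575 (10.1-11.0% of the Phase 2 row) and a cohort proportion with a half-width of about 4 points or less at an assumed 30% rate (3.7 at n = 575, 4.2 at n = 455), if all clients answer.

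This is worth changing but does not touch the primary safety endpoint. It assumes that the forms whose tables are not visible in the available text, chiefly the placement and follow-up log (Appendix XV) and the removal time form (Appendix XXI), contain no erection or removal comfort item.

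**What to change.** 1. Add two items to Appendix XI on the response scale of its item 1: discomfort during erections while wearing the ring, and discomfort during the removal. Allow an answer for clients who had no erections, so that the denominator is clear.
2. Put the same intensity scale beside Appendix X item 3 and keep the expectation question.
3. Reconcile the Appendix XII instruction on the pain score with the Photography section, and give the score before and after removal its own field on the follow-up form, so that it does not depend on a photograph.
4. Report each item as a proportion with a 95% confidence interval, with a descriptive split by age 13-17 and 18 or over. The documents do not give the age mix, so precision within age groups cannot be stated in advance.

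The cost is three short survey items and one form field, at the placement and removal visits that every client is already asked to attend. The interviews can stay as they are and explain the numbers.
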